Official Title: Adaptive Ankle Robot Control System to Reduce Foot-drop in Chronic Stroke

NCT02483676

April 12, 2019

Statistical Analysis Plan for the study of Ankle Robot to Reduce Foot Drop in Stroke

This document lays out the analysis plan we intend to use for the study of whether robot-assisted treadmill training will result in greater improvements in gait and balance among chronic stroke survivors with foot drop impairment.

1.0 Brief description of the design of the parent study.

After baseline data collection, eligible patients were randomized to receive either treadmill with anklebot (TMR) or standard treadmill TM alone. Randomization was based on permuted blocks in two strata defined by baseline gait speed. Subjects in each group were be expected to attend 3 sessions per week for six weeks. Follow-up data collection will occur at the end of the training session. Durability of the improvements will be measured by also collecting data 6 weeks and 6 months after the end of the intervention. The primary outcomes will be the outcomes measured immediately after the end of training.

2.0 Statistical Test of the Primary Hypotheses.

2.1 Outcomes. The main outcomes to be considered will be::

AIM 1

- peak DF swing angle (Var="Pk DF P-ank) (Primary Outcome)
- DF angle at foot strike (Var="AIC") (2nd Primary Outcome)
- Mean Gait Velocity (Var="Prefered Gaid Velocity w/o AD")
- A-P GRF Propulsion (Var="AP impulse")

AIM 2

- Extent of Postural Sway (Var="EO Sway Area" or "EC Sway Area")
- Peak paretic A-P forces during push-off nonparetic gait initiation (Primary Outcome for Aim 2. (Var="Gait Initiation Peak NP A-P force") (Not collected for last 10-15 patients)

All these outcomes will be treated as quantitative random variables.

2.2 Analysis Sample. The primary analysis will be based on the principle of intention to treat. That is, in the analysis, patients will be included in the group to which

they were randomized, irrespective of whether they actually received the intervention. This provides anunbiased estimate of the causal impact of assigning a patient to TMR vs. assigning them to TR. The principle of intention-to-treat will be violated to the degree that outcomes for some patients at some timepoints are missing. The implications of missing data and how we will handle that are discussed below. Secondary analyses (described below) will be performed to using different analysis samples to estimate different causal parameters.

2.3 Statistical Model. To estimate the impact of TMR vs TR, for each outcome, we will fit the following model:

E(Outcome)= β_0 + β_1 F1 + β_2 F2 + β_3 F3 + β_4 F1(TMR) + β_5 F2(TMR) + β_6 F3(TMR) + β_6 F3(TMR) + β_6 Covariates)

where F1, F2, and F3 are indicators for the three follow-up measures, and TMR is an indicator that the patient was in the TMR group. In this model, β_4 , β_5 , and β_6 stand for the difference between TMR and TR at each of the three follow-up time points. The primary analysis will be based on β_4 . This model will be fit using restricted maximum likelihood, allowing for different variancs at each time point, and different covariances between any two time points (this is sometimes referred to as an "unstructured" variance/covariance assumption). We will allow a different variance/covariance structure in each intervention group. However, if the differences in the estimated variance/covariance structures are not statistically significant (based on a likelihood ratio test), we will assume a common variance/covariance structure in the final model.

This model will provide valid inference if the distribution of outcomes does not markedly depart from normality. If an outcome appears to depart from normality by exhibiting a great deal of positive skewness (e.g., skewness coefficient greater than 3.0), I will fit the above model using a log-tranformed version of the outcome.

2.4 Covariates. Covariates will be included in the model if they are statistically significant (p<0.05) predictors of the outcome. This will reduce residual variation and increase power. Up to 3 covariates will be included in the model based on the strength of their statistical significance, chosen in a forward stepwise manner. Covariate will be chosen from the following candidate variables.

Time Since Stroke Age Sex Wearing an AFO Non-AFO AD SIS mobility Baseline Gait Velocity (cm/sec) Baseline Peak Paretic DF Swing Angle (deg) Baseline Paretic DF Angle at Foot Contact (deg) Baseline Paretic A-P Propulsion in Late Stance (N-s) Baseline CoP Sway Area (cm2) Baseline Standing asymmetry (NP/P vertical forces) Baseline Peak Paretic A-P force during gait initiation (N) **2.5 Impact of Missing Outcomes.** The methods described above will result in unbiased estimates of the impact of being assigned toTMR assuming that the data are missing at random, given all observed data. That means, essentially, that conditional on all observed outcomes, the distribution of the missing outcomes is not different than the distribution of the observed outcomes. However, if there are departures from the missing-at-random assumption (e.g., if those with the worst outcomes are the ones who fail to return for follow-up visits), then the estimated rates of improvement may be biased. Note, however, that the estimated treatment effect would only be biased if there were differential degrees of departure from the missing-at-random assumption in the two treatment groups.

The proposed approach is somewhat resistant to biases due to missing data because it is based on maximum likelihood estimation and takes into consideration all the observed data. Thus, for example, if a patient has missing outcomes for the second follow-up visit, but has been observed at other time points, the estimation of the outcomes at the second follow-up will be implicitly imputed based on the observed outcomes and the included covariates.

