We chose the sample size (36 subjects completing the training per group) to have good power to detect moderate effects of the TMR at the post-training assessment. More specifically, with a sample size of 36 per group we will have 85% power to detect a difference between the groups if the mean changes in the two groups differ by 0.72 standard deviations (i.e., an "effect size" of 0.72). This calculation is based on the performance of a two-sided .05-level two sample t-test. This is a conservative projection of the power because the actual analysis will be based on a mixed effects model for repeated measures, and will be slightly more powerful than a t-test. Note an effect size of 0.72 is considerably smaller than the effect sizes we observed for the response variables in our pilot data as shown in the following table. Thus, we believe the study is adequately powered even if our findings in the proposed study are somewhat less striking than those observed in our pilot study. If we want to control the experiment-wise type-1 error rate at 0.05 we will have to test each hypothesis at the 0.007 level (to adjust for multiple comparisons). This will result in 85% power to detect on effect size of 0.90. Note that this detectable effect size is still considerably smaller than the effects observed in our pilot study for all variables except gait velocity.
- 2 * Provide the plan for data analysis. Include in the description the types of comparisons that are planned (e.g., comparison of means, comparison of proportions, regressions, analysis of variance, etc.), which is the primary comparison/analysis, and how the analyses proposed will relate to the primary purposes of the study:

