5.1 If Yes, what procedures are in place to assure safety?

ID: VIEW4E09460F5EC00
Name: v2_Surveys/Questionnaires

View: v2_Data Collection / Record Review

Data Collection/Record Review

You indicated on the "Type of Research" page that your study involves data collection or record review (i.e., chart review, not self-report).

1 * What type of data will be collected/analyzed in this study? (Check all that apply)
Prospective (data is not yet in existence and/or collected)

2 * Will this study involve adding data to a registry or database for future use?
 Yes No

3 * Will the data be released to anyone not listed as an investigator on the protocol?
 Yes No

3.1 If Yes, give name(s) & affiliation(s):

ID: VIEW4E0E25A8CA400
Name: v2_Data Collection / Record Review

View: v2_Pro prospective Data

Prospective Data

You indicated that the study involves the collection of prospective data.

1 * Where is the data being collected from? (Check all that apply)
Medical records
Other

1.1 If Other, please specify:
Functional gait and balance assessments and other training data related to the proposed interventions.

2 * What data fields will you have access to/collect for the study? For example, name, initials, date of birth, Social Security number, income, demographic information, family units, housing, etc.
Name
Date of birth
Soc Sec (for VA forms only)

You can also upload a copy of the data fields/variables to be collected for the study:

Name	Created	Modified Date
There are no items to display		

ID: VIEW4E0E25B643800
Name: v2_Pro prospective Data

View: v2_Clinical Trial Registration

Clinical Trial Registration

You indicated on the "Type of Research" page that your study is a clinical trial.

1 * Does the UM Clinical Trials Registry policy require registration of this trial?
 Yes No

2 * Has this trial been registered?
 Yes No

ID: VIEW4E093BF078C00
Name: v2_Clinical Trial Registration

View: v2_Participant Selection

Participant Selection

1 * How many local potential participants (or specimens/charts) do you anticipate will be screened for this study? **Screening includes determining potential participants' initial eligibility for and/or interest in a study.**
150

- 2 * How many participants (or specimens, or charts) will be enrolled/used for this study? **A local prospective participant is considered enrolled in the study when a UM-approved Informed Consent Document (not including separate screening consent forms) is signed.**

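### Does the gap of 10-15 patients in the Aim 2 primary outcome require the SAP to restate sample size and power?

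*SAP*

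**What the plan says.** The protocol's Sample Size and Data Analysis section, item 1, sizes the trial on 36 patients per group who complete training. It states that "with a sample size of 36 per group we will have 85% power to detect a difference between the groups" at a difference of 0.72 SD in mean change, using a two-sided 0.05-level two-sample t-test. For the case where the experiment-wise error rate is to be controlled, it adds a figure at the 0.007 level: "This will result in 85% power to detect on effect size of 0.90". It calls the t-test basis conservative because "the actual analysis will be based on a mixed effects model for repeated measures, and will be slightly more powerful than a t-test".

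SAP 2.1 names peak paretic A-P force at gait initiation as the primary outcome for Aim 2 and records the gap on the same line: "Var='Gait Initiation Peak NP A-P force') (Not collected for last 10-15 patients". SAP 2.2 concedes in general terms that "The principle of intention-to-treat will be violated to the degree that outcomes for some patients at some timepoints are missing". SAP 2.5 sets out the missing-at-random assumption and the likelihood approach. SAP 2.4 allows up to three covariates, with the reason that "This will reduce residual variation and increase power". The SAP states no sample size or power for any outcome.

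**The concern.** The only power figures in the documents rest on 36 patients per group, and a t-test on change needs the outcome measured in each of them. A designated primary outcome then turns out to be missing for 10 to 15 patients. The gap is given as a range, and no reduced number or detectable effect goes with it.

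The general missing-data text does not obviously cover the case. SAP 2.5 discusses bias, not precision, and its example is a patient seen at other visits. A patient with no value of this outcome at any visit adds nothing to a model fitted to that outcome alone.

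At stake is how a null Aim 2 result is read. A reader who carries the 85% over from the protocol may credit this comparison with more precision than it has.

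**Working it through.** **Inputs.** From the protocol: 36 per group, 0.72 SD, two-sided 0.05, t-test. From SAP 2.1: 10 to 15 patients without the outcome. From SAP 1.0: "Randomization was based on permuted blocks in two strata defined by baseline gait speed", which supports a near-equal split of the loss between arms.

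**Method.** Noncentral t with n1 + n2 − 2 degrees of freedom and noncentrality d / √(1/n1 + 1/n2).

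**The protocol's own figure.** With 36/36 and d = 0.72, the noncentrality is 0.72 / √(2/36) = 3.05 and power is 85.4%. The second figure (0.007 level, d = 0.90) gives 84.7%. Both reproduce.

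**The loss on the t-test basis**, assuming exactly 72 completers and that patients without the measure contribute nothing:

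| Measured | Split | Noncentrality | Power at 0.72 SD | Detectable effect, 85% power | SE relative to 72 |
|---|---|---|---|---|---|
| 72 | 36/36 | 3.05 | 85.4% | 0.72 SD | 1.00 |
| 62 | 31/31 | 2.83 | 79.6% | 0.77 SD | √(72/62) = 1.08 |
| 57 | 29/28 | 2.72 | 76.1% | 0.81 SD | √(72/57) = 1.12 |

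If the whole loss fell in one arm, which permuted blocks make unlikely, power would be 78.6% (36/26) to 73.1% (36/21).

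**How this depends on the number of completers.** The documents do not give that number. The 100 in Participant Selection is a consent count ("A local prospective participant is considered enrolled in the study when a UM-approved Informed Consent Document" is signed), so it is only an upper bound. The bases of 60 and 80 are assumptions.

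| Completers | Power at 0.72 SD, 15 to 10 missing |
|---|---|
| 60 | 66% to 70% |
| 72 | 76% to 80% |
| 80 | 82% to 84% |
| 100 | 91% to 92% |

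The loss is fully absorbed at 72 + 10 = 82 to 72 + 15 = 87 completers.

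**The planned model.** SAP 2.3 treats baseline as one of the repeated measures and has no group term at baseline. With equal variances σ² and baseline-to-post correlation r, a change-score comparison has variance proportional to 2σ²(1 − r). The SAP model has variance proportional to σ²(1 − r²). The ratio is (1 + r)/2, so 0.72 SD of change acts like 0.72 / √((1 + r)/2): 0.831 at r = 0.5, 0.781 at r = 0.7 and 0.739 at r = 0.9. The values of r are assumptions, and SAP 2.4 covariates are left out.

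| Measured | r = 0.5 | r = 0.7 | r = 0.9 | Largest r that keeps 85% |
|---|---|---|---|---|
| 62 | 90% | 86% | 82% | 0.73 |
| 57 | 87% | 83% | 78% | 0.59 |

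The break-even r solves 0.72 / √((1 + r)/2) = detectable effect. For 62 measured, r = 2 × (0.72/0.7736)² − 1 = 0.73. For 57, r = 2 × (0.72/0.8081)² − 1 = 0.59.

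**The case for a change.** The strongest case for a change is that this is the single primary outcome of Aim 2, that its precision is stated nowhere, and that the remedy is a count and a few sentences. The protocol calls the mixed model only slightly more powerful and gives no correlation, so its gain cannot be relied on. At r = 0.9, 72 completers with 57-62 measured would leave 78-82%. No document gives the number completing, so nobody can tell from the text whether the loss was absorbed.

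All of that is true, and it stands as an argument for clear reporting. It does not show that the plan is wrong. The uncertainty runs in both directions: the same missing figures that prevent a claim of 85% also prevent a claim of less. Power is a planning quantity, and restating it once the gap is known alters no estimate, test or analysis set. The analysed number per arm and the confidence interval tell a reader how precise a null result is, and both come out of the planned analysis.

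The 0.007-level figure does not strengthen the case. The protocol offers it conditionally, and the SAP does not adopt that level.

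**Conclusion.** No change to the plan. The protocol's power statements are correct for 36 completers per group, and SAP 2.1 discloses the gap beside the outcome it affects. The missing detail concerns precision; no bias has been shown.

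The plausible size is a fall from 85% to 76-80% power at 0.72 SD and a standard error 8-12% larger. That rests on three assumptions: exactly 72 completers, a near-equal split of the loss, and a plain t-test. The third is not the planned analysis, and the first is not established. With 82-87 completers, or under the SAP 2.3 model with a correlation up to about 0.73 (62 measured) or 0.59 (57 measured), 85% is kept.

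An analyst who follows the SAP as written will fit the same model to the patients who have the outcome. The ordinary results report should then give the exact number without it, by arm and visit, and the analysed number per arm with a confidence interval.

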3.0 Secondary Analyses

3.1 Intention to treat analysis of secondary outcomes. Similar analyses will be performed to explore the impact of TMR on the following secondary outcomes:

AIM 1

- Single support duration (Var="P-SS%")
- Double support duration (Var="DS%")
- Timing of peak fexion (Var="PK DF P-ank %cyc")
- Pareti foot vertical clearance (Var="p-foot clearance")
- Steps/day in two consecutive days (Var="48 hr Step Count ") (There seems to have been a lot of non-adherence regarding this measure and it may not be usable)
- Stroke Impact Scale (Var="SIS Mobility")

AIM 2

- coP trajectories of APAs during gait initiation by leg (Not measured)
- Berg Balance Scale (Var="Berg Balance")
- DGI scale (Var="DGI")
- ABC Scale (Var="ABC")

3.2 Per Protocol Analysis. In a secondary set of analyses, we will perform all of the above described analyses after including only those patients who attended at least 15 sessions in their assigned group. This results in an estimate of the causal impact of the TMR (relative to TM) among those willing and able to come to most of the sessions. We would expect to see a somewhat greater effect of TMR in this analysis because it will remove those who did not attend the TM sessions.

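### SAP 2.3 and 2.4 together let an outcome's own baseline be both response and covariate in one model; if it is selected, the REML fit has no maximum

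*SAP*

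**What the plan says.** **Model.** SAP 2.3 gives a mean with an intercept, three visit indicators and their products with the TMR indicator: "where F1, F2, and F3 are indicators for the three follow-up measures". There is no TMR main effect. The fit is by REML with an unstructured covariance, and β4 is the primary contrast. On the covariance, the SAP says: "We will allow a different variance/covariance structure in each intervention group". If the difference in "variance/covariance structures are not statistically significant (based on a likelihood ratio test), we will assume a common variance/covariance structure". An outcome is logged only when it is "exhibiting a great deal of positive skewness (e.g., skewness coefficient greater than 3.0").

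**Covariates.** SAP 2.4 sets the entry rule: "Covariates will be included in the model if they are statistically significant (p<0.05) predictors of the outcome". Up to three are "included in the model based on the strength of their statistical significance, chosen in a forward stepwise manner". The candidate list includes "Baseline Peak Paretic DF Swing Angle (deg) Baseline Paretic DF Angle at Foot Contact (deg"), which are the baselines of the two Aim 1 primary outcomes in SAP 2.1. It also appears to include the baselines of the other main outcomes, though the labels match less exactly:

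- gait velocity is listed without the assistive-device condition;
- sway is listed without the eyes-open or eyes-closed condition;
- gait-initiation force is paretic in the candidate list, but NP in the outcome's variable name;
- SIS mobility, also a secondary outcome in SAP 3.1, is a candidate without the word baseline.

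**Time points and strata.** The Protocol (Sample Size and Data Analysis, question 2) counts baseline among the analysed time points. SAP 1.0 and the Protocol's randomization paragraph both stratify on gait speed. The stratum is neither a model term nor a candidate. Continuous baseline gait velocity is only an optional candidate.

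**The concern.** If baseline is a response and the same variable is also a covariate, a coefficient of 1 and an intercept of 0 reproduce the baseline row exactly. The unstructured covariance leaves the baseline residual variance free, so it can shrink to zero and the likelihood grows without limit. Software will then either fail or stop at an arbitrary point.

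The SAP's rule for choosing between common and group-specific covariance compares two such likelihoods, so it loses its meaning as well. What is at stake is that the pre-specified primary fit could not be carried out as written, and an unplanned decision would be taken with the data in view.

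The missing stratum term is a separate and smaller matter of matching the analysis to the design.

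**Working it through.** **1. The plan's own figure.** Protocol inputs: 36 per group, difference 0.72 SD of change, two-sided 0.05 t-test. The noncentral t gives 85.4%, so the stated 85% is reproduced. At 0.90 SD and level 0.007 it gives 84.7%. Nothing below changes these figures.

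**2. Is baseline a response row?** Count each distinct term of SAP 2.3 once: intercept, F1 to F3, and F1 to F3 by TMR make 7 columns. On follow-up rows alone the intercept equals F1 + F2 + F3, so the rank is 6 of 7. With the baseline row added it is 7 of 7. Together with the Protocol's list of time points, this favours four rows. If only follow-up rows were meant, adding the own baseline gives rank 7 of 8; β4 is estimable and there is no problem.

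**3. Why there is no maximum.** Let s be the baseline residual SD and n = 72. The baseline row contributes −n ln s. Two mean parameters (intercept and own-baseline slope) are absorbed by that row, which gives back +2 ln s. The quadratic term stays finite because the slope moves to 1 as s falls. The REML log-likelihood therefore behaves as −(n − 2) ln s and rises by 70 × ln 10 = 161.2 per tenfold fall in s.

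Check on one simulated data set: 36 per group, four visits, complete data, equal correlation ρ = 0.6 between visits (assumed; the documents give none), effect 0.5 SD.

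| s | common covariance | group-specific |
|---|---|---|
| 1 | −298.6 | −294.8 |
| 0.1 | −137.4 | −133.6 |
| 0.01 | 23.8 | 27.6 |
| 0.001 | 185.0 | 188.8 |
| 0.0001 | 346.2 | 350.0 |

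Every step is 161.2.

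**4. The likelihood ratio test.** At matched s the statistic is 2 × 3.8 = 7.6. If the two fits stop at different s, it shifts by 2 × 70 × ln(ratio of SDs), or 322.4 for a tenfold ratio. The 5% critical value on 10 df (20 covariance parameters against 10) is 18.31. A ratio of exp(18.31/140) = 1.14 shifts the statistic by that whole amount.

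**5. Would the own baseline be selected?** In the four-row model its t statistic is 37, 430, 4248, 42539 and 432142 at the five values of s above, so it outranks any other candidate. If candidates were instead screened on the post-training value alone, the chance of p < 0.05 is Φ(atanh(ρ) × √69 − 1.96): 73%, 94% and 99.5% at ρ = 0.3, 0.4 and 0.5.

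**6. Effect on β4, against the same fit without the own baseline.** SEs are model-based.

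- *Common covariance*, 100 data sets at each of ρ = 0.4, 0.6 and 0.8: largest change 0.013 SD, SE ratio about 1.005.
- *Group-specific, both groups at the same s*, 40, 40 and 60 data sets at those ρ: largest change 0.024 SD; median SE ratios 1.25, 1.15 and 1.34, with maxima 2.6, 3.0 and 2.8.
- *Group-specific, s differing tenfold between groups*, 15 data sets: β4 moved by up to about 0.08 SD. In one data set the SE ranged from 0.43 to 0.57, against 0.23 without the own baseline.

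A logged outcome with its raw baseline as covariate gave a finite maximum (baseline residual SD 0.43, against 0.89 for the logged baseline itself).

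**7. Stratum.** Under stratified blocks the estimator's variance is (1 − R²) times the full variance whether or not the stratum is modelled, but the SE uses the full variance when it is omitted. At 0.72 SD, power with the stratum rises from 86.0% to 87.1% (R² 0.05, assumed) and from 86.6% to 88.8% (R² 0.10, assumed). If baseline is already adjusted for, the gain is 0.5 to 1.8 points.

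In the four-row model, one stratum coefficient for all visits raised the SE of β4 for gait velocity by factors of 1.075, 1.051 and 1.034 at ρ = 0.4, 0.6 and 0.8. With a stratum-by-visit interaction the factors were 0.998 to 1.001. For other outcomes at ρ = 0.6 and partial R² 0.05 to 0.10, the factors were 0.949 to 0.986 with one coefficient and 0.944 to 0.972 by visit.

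**The case against.** The defect is conditional. It needs four response rows, an untransformed outcome and selection of the own baseline. SAP 2.4 permits that selection without requiring it, from one candidate pool shared by all outcomes. The printed formula has visible slips (a repeated term and a reused coefficient), so counting its columns is not conclusive. Listing baselines as covariates also fits a follow-up-only reading. These limits stand. The four-row reading remains the more natural one because the Protocol names baseline as an analysed time point, and on that reading the selection rule favours the harmful variable.

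The larger SEs come from group-specific fits to data simulated with no group difference in covariance. A working likelihood ratio test would keep the common structure in about 95% of such trials. This also stands: the SE ratios matter only if the group-specific structure is kept. They do not remove the problem, because the test that should make the choice is the one left undefined.

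A reader might infer that the fit collapses to a change-score comparison and loses power. That limit appears only when the covariance between baseline and follow-up is held at zero, and SAP 2.3 leaves it free. In one common-covariance run β4 was 0.712, against 0.714 without the own baseline and 0.536 for the change score.

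**Conclusion.** The point holds in conditional form. On the natural reading of SAP 2.3, selecting an outcome's untransformed own baseline leaves the REML fit without a maximum and the covariance test without a value. This follows from algebra and does not depend on the assumed correlations. It applies clearly to both Aim 1 primary outcomes and less certainly to those with unclear labels. It does not apply to follow-up-only models, to a logged outcome with a raw covariate, or where the own baseline is not listed or not selected.

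The likely numerical harm to β4 is small with a common covariance. It is larger, and dependent on the stopping point, if group-specific covariance is kept. Those sizes rest on assumed correlations of 0.4 to 0.8, equal between visits, and complete data.

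A reader might infer that the primary analysis must fail, or that β4 will be seriously biased. The documents support neither: selection is permitted, not mandatory, and β4 moved by at most about 0.02 SD when both groups stopped at the same baseline SD. Nor does the missing stratum support a claim of bias or inflated type I error; it costs a little precision. The first part should be fixed because the primary analysis ought to be executable as written. The second is minor.

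**What to change.** (a) Add to SAP 2.3/2.4: *Each outcome's baseline is used once, as a response row; it is not eligible as a covariate in that outcome's own model.* Naming the variable for each outcome would also settle the unclear labels (device condition, eye condition, NP or paretic force, SIS mobility). This restores a finite maximum and a usable likelihood ratio test, and needs only wording.

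(b) Separately, and minor: *The gait-speed randomisation stratum and its interaction with visit are included in every model and do not count towards the three selected covariates.* This costs four mean parameters per model (stratum plus three stratum-by-visit terms). The alternative is a single stratum term, at one parameter, with a statement that the gait-velocity model omits it because its baseline row already carries that information.

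Neither change needs new data or drops a patient. Whether stepwise selection should be used at all is a different question, which this fix leaves alone.

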Data are analyzed for normality and transformed as necessary. Robust and resistant analyses or non-parametric analyses are performed as required. Analyses of effects of interventions on gait and balance outcomes are performed using repeated measures group-by-time (GxT) ANOVA for data obtained at baseline, after 6-weeks training, and at 6-weeks and 6-months post-completion of training. Non-parametric statistics are used when appropriate. Post hoc testing is performed using Scheffe's test. Because traditional ANOVA and regression analyses eliminate subjects who are missing data from one or more time points these analyses are performed using SAS PROC MIXED that allow subjects with incomplete data to be included. Initial analyses are intention-to-treat. Subsequent analyses take compliance into account. Baseline data are used to examine predictors of treatment response. We include data analyses for each method to avoid redundancy.

ID: VIEW4E02806052800
Name: v2_Sample Size and Data Analysis

View: v2_Sharing of Results

Sharing of Results

- 1 * Describe whether results (study results or individual subject results, such as results of investigational diagnostic tests, genetic tests, or incidental findings) will be shared with subjects or others (e.g., the subject's primary care physicians) and if so, describe how it will be shared:
Typically quantitative results from robotic results and other functional measures will not be shared with the participant. If a medical problem is revealed during medical examination and screening the participant will be informed and study staff will make appropriate efforts to facilitate follow-up with the participant's primary care physician.

ID: VIEW4E02808C8D800
Name: v2_Sharing of Results

View: v2_Research with Medical Devices

Research with Medical Devices

You indicated on the "Type of Research" page that your study involves the evaluation of device(s) for safety or effectiveness or use of a HUD.

- 1 * List all devices to be used in this study:

Device Name	FDA Approved?	Labeled	IDE Number	IDE Holder
View IMT Anklebot	yes	yes	N/A	no
- 2 * Attach the device labeling or device manual for the devices being used in this study:

Name	Created	Modified Date
Anklebot manual	1/20/2015 2:05 PM	1/20/2015 2:05 PM
- 3 * Are you requesting a nonsignificant device risk determination by the IRB? (Applicable if the FDA has not issued an IDE and the device does not qualify to be IDE exempt.)
 Yes No

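### Each covariate has one coefficient shared by baseline and follow-up, so the power gain promised in SAP 2.4 is not assured, is usually small, and can reverse

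*SAP*

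**What the plan says.** The SAP 2.3 mean model has an intercept, three visit indicators, a TMR term at each follow-up and a covariate term. It explains the symbols thus: "where F1, F2, and F3 are indicators for the three follow-up measures, and TMR is an indicator that the patient was in the TMR group". There is no TMR main effect. With indicators for follow-up visits only, the intercept can be estimated only if baseline is itself a response row. The protocol's data analysis section agrees, since its repeated-measures analysis is "for data obtained at baseline, after 6-weeks training, and at 6-weeks and 6-months post-completion of training".

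The covariates enter at the end of the formula as "β_6 F3(TMR) + β_6 Covariates", with no product of covariate and visit. (Reusing the label β_6 is a slip of notation.) The covariance is unstructured, with "different covariances between any two time points". On the contrast of interest: "The primary analysis will be based on β_4".

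SAP 2.4 admits covariates that reach p<0.05: "Up to 3 covariates will be included in the model based on the strength of their statistical significance, chosen in a forward stepwise manner". The reason given is "This will reduce residual variation and increase power". No size is given for the gain, and no condition is attached to it.

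**The concern.** A covariate with the same effect at baseline and follow-up describes a patient's overall level. The baseline row already carries most of that information into the estimate of β4 through the unstructured covariance. The significance rule therefore rewards prediction of level, whereas β4 gains precision only from what a covariate says about the end-of-training outcome once baseline is known.

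If the covariate's effect is weaker after training than before, the model must compromise on one coefficient. That coefficient is too small at baseline and too large at follow-up, and the mismatch becomes noise in the primary contrast. A covariate can then be clearly significant and still widen the confidence interval. With 36 completers per group, a stated power gain that may be a loss is worth removing.

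**Working it through.** **Inputs from the documents.** 36 completers per group; effect 0.72 SD of change; two-sided 0.05; 85% power by two-sample t-test (protocol, sample size section). Four visits and an unstructured covariance (SAP 2.3).

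**Assumptions, because the documents give no figures.** Unit variance at each visit; one correlation ρ between any two visits, 0.6 to 0.8; one standardised covariate X correlated a0 = 0.5 with baseline and a1 with each follow-up; complete data; X measured before randomisation and not the outcome's own baseline.

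**The plan's own figure.** Noncentral t power with 36 per arm is 85.4% at 0.72 SD and 0.05, and 84.7% at 0.90 SD and 0.007. Both stated values of 85% are reproduced. They refer to a t-test on change, not to the mixed model.

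**Formulas.** Var(β4) is proportional to:
- no covariate: V0 = 1 − ρ²
- as written: V1 = Var(Y1 − gX | Y0 − gX) = r11 − r01²/r00, where r00 = 1 − 2g·a0 + g², r01 = ρ − g(a0 + a1) + g², r11 = 1 − 2g·a1 + g², and g minimises the determinant of the 4 × 4 residual covariance
- visit-specific coefficients: V2 = Var(Y1 | Y0, X), which cannot exceed V0

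**Case 1, constant effect (a1 = 0.5).** Here g = 0.5. At ρ = 0.7, V1 = 0.75 − 0.45²/0.75 = 0.480 against V0 = 0.510, a fall of 5.9%. At ρ = 0.6 and 0.8 the falls are 8.3% and 3.7%. V2 equals V1. X explains 25% of outcome variance, but most of that is already in the baseline row.

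**Case 2, nothing beyond baseline (a1 = ρ × 0.5).** At ρ = 0.7, a1 = 0.35 and g = 0.411, so r00 = 0.758, r01 = 0.520, r11 = 0.881 and V1 = 0.525, a rise of 2.9%. At ρ = 0.6 and 0.8 the rises are 3.5% and 2.2%. V2 = V0.

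**Case 3, sharp drop after training.** X is given a negative effect on follow-up that explains 10% of the variance left after baseline. At ρ = 0.7 the partial coefficient is −√(0.10 × 0.51/0.75) = −0.261, so a1 = 0.35 − 0.261 × 0.75 = 0.154. Then g = 0.343, r00 = 0.775, r01 = 0.593, r11 = 1.012 and V1 = 0.557, a rise of about 9%. At ρ = 0.6 (a1 = 0.08) it is also about 9%, and at ρ = 0.8 (a1 = 0.24) about 8%. V2 is 10% below V0.

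**Power.** With the effect fixed at d = 0.72 × √(2(1 − ρ)), z = d/√(2V/36) and power = Φ(z − 1.96). At ρ = 0.7, d = 0.558:

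| | V | Power |
|---|---|---|
| Change score | 0.600 | 86.3% |
| No covariate | 0.510 | 91.2% |
| Case 1, as written | 0.480 | 92.7% |
| Case 2, as written | 0.525 | 90.4% |
| Case 3, as written | 0.557 | 88.7% |

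The case 2 loss is 0.6 to 0.8 points over ρ = 0.6 to 0.8. The case 3 loss is about 2.5 points by this algebra. With the 12% variance inflation seen in simulation (2,500 REML fits), power is 87.9%, a loss of 3.3 points.

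**Simulation of the four-visit REML model (36 per arm, 600 replicates per scenario, ρ 0.5 to 0.85, a0 0.3 to 0.5).** When X added nothing beyond baseline, it was still significant in 58-99% of trials, and the interval for β4 was wider than without X in 66-85%. When the correlation grew from 0.3 at baseline to 0.5 at follow-up (ρ = 0.7), the written model did gain: the mean SE fell from 0.1659 to 0.1532 and power rose from 90.3% to 94.5%.

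**The case against.** The strongest reply is that the plan often does what it says. With a constant effect the shared coefficient is correctly specified and slightly better than visit-specific terms: in the 2,500-fit simulation the variance ratios were 0.94 and 0.96. With an effect that grows after baseline the gain is material. This stands. A reader might infer that the promised gain is simply not delivered; the documents and the arithmetic do not support that.

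A reader might also infer that power falls below the 85% design target. That does not follow. The 85% belongs to a change-score t-test, and the protocol itself expects the mixed model to do better. At 0.72 SD of change the mixed model starts near 91% at ρ = 0.7 and stays above 85% even in case 3.

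Case 3 is demanding. It needs a correlation of 0.5 to fall to about 0.15 after training. Patients with a better value on the outcome itself gaining less would not produce this, because the unstructured covariance already absorbs it. Nothing in the documents shows such a pattern, so case 3 is an upper illustration and case 2 the ordinary loss.

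Finally, the candidate list contains the baseline values of the main outcomes, and stepwise selection would probably take an outcome's own baseline first. That is a separate problem, outside the cases above. If it were solved by dropping the baseline row and adjusting for baseline, the shared coefficient would no longer span baseline and this point would fall away.

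**Conclusion.** The point holds as one of efficiency. The unconditional statement in SAP 2.4 is not supported: the gain depends on how each covariate's effect changes from baseline to follow-up, which the written model cannot represent and the p<0.05 rule does not check. For a covariate correlated 0.5 with baseline, the change in Var(β4) runs from a fall of 4-8%, through a rise of about 2-4%, to a rise of about 8-9% in the extreme case. In power, the losses are about 1 point or less and about 3 points.

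No bias in β4 and no type I error inflation is claimed for this feature. Covariates fixed before randomisation are independent of arm, so a poorly fitting coefficient costs precision only. The figures rest on the assumed correlations, equal correlation between visits, complete data, one covariate at a time, and reading the significance test in SAP 2.4 as applied within the model of SAP 2.3.

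**What to change.** In SAP 2.3, replace the single covariate term for each covariate with the covariate plus its products with F1, F2 and F3, or plus one product with a post-baseline indicator (1 df). In SAP 2.4, name two or three covariates in advance, none of them the outcome's own baseline while baseline stays a row, and drop the stepwise choice. Reword the power statement to say that a gain is expected only from covariates that predict follow-up beyond baseline.

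With the three products, the asymptotic variance of β4 cannot exceed that of the model without covariates. For the 1-df form this guarantee needs the covariate's effect to be similar at the three follow-ups. In simulation at ρ = 0.7 both forms turned the case 3 loss into a 9-11% fall in variance.

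The cost is SAP wording and 1 to 3 extra parameters per covariate, at most nine for three covariates. When the terms are not needed, they cost about 0.5-2% of variance per covariate. Three covariates together with missing visits were not simulated, which favours the 1-df form or fewer covariates.
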